8.6.3 Summaries of Demographic and Baseline Characteristics

The comparability of the treatment groups for each relevant characteristic will be assessed by the use of tables and/or graphs. No statistical hypothesis tests will be performed on these characteristics. The number and percentage of subjects screened, randomized, the primary reasons for screening failure, and the primary reason for discontinuation will be displayed. Demographic variables (e.g., age), baseline characteristics, primary and secondary diagnoses, and prior and concomitant therapies will be summarized by treatment either by descriptive statistics or categorical tables.

8.7 Interim Analyses

There are 2 planned interim analyses in this trial in addition to the final analysis. Results will be reviewed by an eDMC.

8.7.1 Efficacy Interim Analyses

The purpose of the first interim analysis is to conduct the main testing for efficacy on the PFS and ORR endpoints and to conduct an interim testing for efficacy on the OS endpoint. It will be performed when approximately 183 OS events (67% of expected total OS events) are observed. With approximately 16 months enrollment, the IA1 is expected approximately at Month 22, at which time approximately 331 PFS events are expected to have been accumulated.

The purpose of the second interim analysis is to conduct the efficacy testing on the OS endpoint if the result of OS endpoint is not successful at the first IA. The second IA will be performed when approximately 232 OS events (85% of expected total OS events) are observed, which is expected at approximately Month 28.

The final analysis (FA) will be performed when approximately 273 OS events are observed which is expected at Study Month 35.

The operating characteristics of conducting the IA for testing the OS hypothesis at 67% and 85% expected total OS information are shown in [Table 14](#). A detailed description of the multiplicity adjustment and hypotheses testing plan is provided in Section 8.8 Multiplicity.

8.7.2 Safety Interim Analyses

As noted in Section 7.3.3 – Data Monitoring Committee, the DMC will be responsible for periodic interim safety reviews as specified in the DMC charter.

8.8 Multiplicity

The multiplicity strategy specified in this section will be applied to the two primary hypotheses (superiority of pembrolizumab on PFS or OS) and the secondary hypothesis of superiority of pembrolizumab in ORR.

The overall Type I error across the testing of the OS, PFS, and ORR hypotheses is strongly controlled at $\alpha=2.5\%$ (one-sided). The multiplicity strategy will follow the graphical approach of Maurer and Bretz [50]. [Figure 3](#) provides the multiplicity strategy diagram of the study.

[figure not shown]

Figure 3 Multiplicity Strategy

In the diagram shown in [Figure 3](#), when a particular null hypothesis is rejected, the arrows leading to it are removed, and the Type I error allocated to the null hypothesis that was rejected is re-distributed to the other two hypotheses. The arrows on the diagram show how the Type I error allocated to a hypothesis that was successfully tested will be re-distributed for the testing of the other two hypotheses. Initially, $\alpha=2.3\%$ ($23/25$ of the overall total $\alpha=2.5\%$ for testing the OS, PFS, and ORR) is allocated to the OS hypothesis and $\alpha=0.2\%$ is allocated to the PFS hypothesis.

The testing of the PFS, OS, and ORR will proceed as follows.

PFS Hypothesis: The testing of the primary PFS hypothesis will be conducted at the time of the first OS IA. The testing of the PFS hypothesis will be based on a PFS test statistic calculated only from study data available at the time of the main PFS analysis at the first OS IA. The PFS hypothesis will initially be tested at Type I error $\alpha=0.2\%$. Depending on the result of the initial testing of the PFS hypothesis and the results of testing of the OS and ORR hypotheses, the PFS hypothesis can be tested at Type I error levels of $\alpha=0.2\%$, $=1.35\%$, or $=2.5\%$. [Table 13](#) shows the boundary thresholds corresponding to a successful testing of the PFS hypothesis at each of these Type I error levels. From [Table 13](#), to declare success on the PFS hypothesis at Type I error $\alpha=0.2\%$, the nominal calculated p-value should be ≤ 0.002 , and the PFS hazard ratio should be ≤ 0.71 . At the time of the main PFS analysis at approximately Month 22, it is expected that 331 PFS events would have been accumulated under assumptions specified in Section 8.9 - Sample Size and Power Calculations.

Table 13 Efficacy Boundaries for Testing the PFS Hypothesis

| Analysis | Study Calendar Time | N ^b | Events | Information Fraction | Efficacy Boundary Crossing | | |
|----------|-----------------------|----------------|--------|----------------------|----------------------------|--------------|--------------------|
| | | | | | Type I Error (α) | Hazard Ratio | Power ^c |
| Primary | Month 22 ^a | 408 | 331 | 1.0 | 0.20% | 0.71 | 99.00% |
| | | | | | 1.35% | 0.77 | >99% |
| | | | | | 2.50% | 0.80 | >99% |

^a The main analysis of PFS will occur based on PFS data at this time. Per the multiplicity adjustment scheme, it is possible for the main analysis PFS test statistic (based on PFS data at this time) to be used again at the time of the second interim OS analysis (Month 28) and end-of-study time point (Month 35) for a re-testing of the PFS hypothesis.

^b Expected number of subjects randomized into the study at the time of analysis.

^c The power calculation is based on the assumptions in Section 8.9.

OS Hypothesis: The OS hypothesis will be tested following a group sequential approach. The testing of the OS hypotheses will be first conducted at approximately Month 22 of the study (i.e., the first IA time point when approximately 183 OS events would have been accumulated). If unsuccessful at the first IA, the OS hypotheses will be tested at the second IA time point when approximately 232 OS events would have been accumulated at approximately Month 28 of the study, and if unsuccessful at the second IA, the OS hypotheses will be tested at the final analysis time point when 273 events will be accumulated at Month 35, approximately. The nominal Type I error rates for the 2 interim analyses and final analysis that will allow tight control of the overall Type I error for testing the OS hypothesis will be derived using the alpha-spending function approach based on the overall Type I error allocated to the OS hypothesis. The group sequential testing of the OS hypothesis will be conducted using the Lan-DeMets spending function that approximates an O'Brien-Fleming boundary. The OS hypothesis will initially be tested at the overall Type I error $\alpha=2.3\%$. If both the PFS and ORR null hypotheses have been rejected at the $\alpha=0.2\%$ level, the OS hypothesis will be tested at a Type I error level of $\alpha=2.5\%$.

[Table 14](#) shows the boundary thresholds corresponding to a successful group sequential testing of the OS hypothesis at each of these Type I error levels. From [Table 14](#), with an overall Type I error $\alpha=2.3\%$, the first interim OS hypothesis testing with 183 events at Type I error $\alpha=0.55\%$ has an associated power of 60% following a group sequential approach under assumptions specified in Section 8.9. For example at overall Type I error $\alpha=2.3\%$, to declare success on the OS hypothesis at Type I error $\alpha=0.55\%$ at the first IA, the OS hazard ratio should be ≤ 0.67 ; to declare success on the OS hypothesis at Type I error $\alpha=1.20\%$ at the second IA, the OS hazard ratio should be ≤ 0.73 ; and to declare success on the OS hypothesis at Type I error $\alpha=1.87\%$ at the final analysis, the OS hazard ratio should be ≤ 0.77 . Conducting the OS hypothesis testing with 273 events at the final analysis at overall Type I error $\alpha=2.3\%$ has an associated power of 91%. The projected interim analyses information fraction of 0.67 and 0.85 will be adjusted according to the proportion of the 273 final planned OS events actually available at the time of the interim analyses. [Table 14](#) shows the example of the hazard ratio boundaries that will be applied if 0.67 and 0.85 of required OS events are observed by the time of the first and second IA, respectively. If the final OS events vary from 273, a minor adjustment in the final bound may be required as well.

The spending function planned to be used for the testing of the OS hypothesis satisfies the requirements laid out in Maurer and Bretz [50].

Table 14 Efficacy Boundaries for Testing the OS Hypothesis

| Type I Error (Overall α) | Analysis | Study Calendar Time | N [§] | Events | Information Fraction | Efficacy Boundary Crossing [†] | | |
|----------------------------------|----------|---------------------|----------------|--------|----------------------|---|--------------|-------|
| | | | | | | Nominal α | Hazard Ratio | Power |
| 2.3% | Interim1 | Month 22 | 408 | 183 | 0.67 | 0.55% | 0.67 | 60% |
| | Interim2 | Month 28 | 408 | 232 | 0.85 | 1.20% | 0.73 | 82% |
| | Final | Month 35 | 408 | 273 | 1.00 | 1.87% | 0.77 | 91% |
| 2.5% | Interim1 | Month 22 | 408 | 183 | 0.67 | 0.62% | 0.68 | 62% |
| | Interim2 | Month 28 | 408 | 232 | 0.85 | 1.32% | 0.73 | 83% |
| | Final | Month 35 | 408 | 273 | 1.00 | 2.02% | 0.77 | 92% |

[†] Based on O'Brien-Fleming spending function. The power calculation is based on the assumptions in Section 8.9.

[§] Expected number of subjects randomized into the study at the time of analysis.

ORR Hypothesis: The testing of the secondary ORR hypothesis will be conducted at the time of the first OS IA. The testing of the ORR hypothesis will be based on an ORR test statistic calculated only from study data available at the time of the main ORR analysis at the first OS IA from all randomized subjects. The ORR hypothesis is initially allocated a Type I error $\alpha=0\%$ and thus, cannot be tested unless one or both of the PFS or OS null hypotheses have been rejected. Depending on the results of the OS and PFS hypotheses testing, the ORR hypothesis can be tested at Type I error levels of $\alpha=0.2\%$, 1.15%, or 2.5%.

Table 15 shows the boundary thresholds corresponding to each of three possible Type I error levels. To declare success on the ORR hypothesis at overall Type I error $\alpha=0.2\%$, the nominal calculated p-value should be $\leq 0.2\%$ (i.e. the Type I error level), and the ORR percentage point difference (pembrolizumab-control) should be $\geq 8.5\%$.

Table 15 Efficacy Boundaries for Testing the ORR Hypothesis

| Analysis | Study Calendar Time | N [‡] | Efficacy Boundary Crossing | | |
|----------|-----------------------|----------------|----------------------------|---------------------------|-------|
| | | | Type I Error (α) | ORR Δ [§] | Power |
| Primary | Month 22 [†] | 408 | 0.20% | 8.5% | 84% |
| | | | 1.15% | 5.8% | 97% |
| | | | 2.50% | 5.0% | 98% |

[‡] Expected number of subjects randomized into the study at the time of analysis.

[§] Δ = ORR in pembrolizumab group – ORR in control group. The assumed expected ORR in pembrolizumab and control groups are 15% and 3%, respectively.

[†] Per the multiplicity adjustment scheme, it is possible for the main analysis ORR test statistic (based on ORR data at this time) to be used again at the second IA (i.e., Month 28) and end-of-study time point (i.e., Month 35) for a re-testing of the ORR hypothesis.

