| Multiplicity | 
The multiplicity strategy in this study will be applied to the 2 primary hypotheses (superiority of pembrolizumab in PFS and superiority of pembrolizumab in OS) and the secondary hypothesis of superiority of pembrolizumab in ORR. The overall Type I error across the 3 hypotheses above is strongly controlled at 2.5% (one-sided). The multiplicity strategy will follow the graphical approach of Maurer and Bretz [50] as described in Section 8.8, with initially 0.2% allocated to PFS hypotheses and 2.3% allocated to OS hypotheses. Within the OS hypothesis that is analyzed following a group sequential approach, the Type I error rates for the interim and final analyses will be controlled through the alpha-spending functions specified for this endpoint as described in Section 8.8. The PFS analysis and the ORR analysis do not use the group sequential approach. The PFS hypothesis is tested using only the PFS data collected at the time of the first interim OS analysis. Similarly, the secondary ORR hypothesis is tested using only the ORR data collected at the time of the first interim OS analysis, whenever the Type I error becomes available for the ORR analysis.
 |

| | |
|------------------------------|--|
| Sample Size and Power | 
The sample size is approximately 408.
 
The analysis of the OS endpoint is event driven. The testing of the OS hypothesis is conducted upon accumulating a preset number of events. The study is designed and will be conducted to accumulate approximately 273 OS events (unless superiority in OS is proven at an interim analysis).
 
For the primary endpoint PFS, the trial is anticipated to have approximately 94% power at the time of the testing of the primary PFS hypothesis to demonstrate that pembrolizumab is superior to the control at a one-sided 0.2% alpha-level, if the underlying hazard ratio of PFS is 0.60.
 
For the primary endpoint OS, the trial has approximately 92% power to demonstrate that pembrolizumab is superior to the control at a one-sided 2.3% alpha-level, if the underlying hazard ratio of OS is 0.65.
 |
|------------------------------|--|

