8.9 Sample Size and Power Calculations

The study will randomize subjects in a 2:1 ratio into pembrolizumab arm and the control arm. Approximately 408 subjects are required to be enrolled in order to test the OS hypothesis at the desired study requirements.

The analysis of the OS endpoint is event driven. The testing of the OS hypothesis is conducted upon accumulating a preset number of events. The study is designed and will be conducted to accumulate approximately 273 OS events.

PFS Analysis: As described in Section 8.7 Interim Analysis, the main PFS analysis will be conducted at the same time as the first OS IA at approximately Month 22 of the study. It is projected that approximately 331 PFS events will be accumulated at this time. With 331 PFS events, the testing of the PFS hypothesis at Type I error $\alpha=0.2\%$ has 94% power to demonstrate that pembrolizumab is superior to the control with respect to PFS if the underlying PFS hazard ratio (pembrolizumab/control) is 0.60.

The power calculation is based on the following assumptions: 1) PFS follows an exponential distribution with a median of 2.5 months in the control arm; 2) An enrollment period of 16 months; 3) a minimum follow-up of approximately 6 months; and 4) A yearly drop-out rate of $\sim 10\%$.

OS Analysis: A total of 273 OS events are required to test the OS hypothesis at Type I error $\alpha=2.3\%$ with $\sim 92\%$ power (see [Table 14](#)) if the underlying OS hazard ratio (pembrolizumab/control) is 0.65. A total of 408 subjects are needed to be enrolled into the study in order to accumulate 273 OS events at approximately Month 35 of the study.

The sample size and power calculation is based on the following assumptions: 1) OS follows a piece-wise exponential distribution with zero hazard during the first month and a median of 10 months in the control arm; 2) An enrollment period of 16 months; 3) a minimum follow-up of 19 months; and 4) A yearly dropout rate of $\sim 2\%$.

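### Table 13 gives 99.00% power for the PFS test at one-sided alpha 0.20%, where Sections 8.1 and 8.9 give 94% for the same test and recomputation supports 94%

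*Combined protocol and SAP*

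**What the plan says.** Three places state the power of the primary PFS test at its initial alpha.

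- **Section 8.8, Table 13.** For the analysis at Month 22 with 331 events, the first row gives alpha, hazard ratio boundary and power as "0.20% | 0.71 | 99.00"%. Footnote c to the power column says: "The power calculation is based on the assumptions in Section 8.9".
- **Section 8.9.** On the event count: "It is projected that approximately 331 PFS events will be accumulated at this time". With those events, the test at alpha 0.2% "has 94% power to demonstrate that pembrolizumab is superior to the control with respect to PFS", "if the underlying PFS hazard ratio (pembrolizumab/control) is 0.60".
- **Section 8.1.** The summary says "the trial is anticipated to have approximately 94% power at the time of the testing of the primary PFS hypothesis", to show that pembrolizumab is "superior to the control at a one-sided 0.2% alpha-level, if the underlying hazard ratio of PFS is 0.60".

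The other two power cells in Table 13, at alpha 1.35% and 2.50%, both read >99%.

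**The concern.** The three statements describe one test: same endpoint, one-sided alpha, hazard ratio and 2:1 allocation, with 331 events in both Table 13 and Section 8.9. Footnote c rules out reading Table 13 as a different scenario. So 94% and 99.00% cannot both be right.

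PFS is one of two primary hypotheses, and Section 3.1 calls the trial positive if either is rejected. The 0.20% row is the level at which PFS is tested first. Someone who takes the power from Table 13 would put the type II error at 1%, where Sections 8.1 and 8.9 imply 6%.

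**Working it through.** **Inputs**

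- One-sided alpha 0.002, so z = 2.878 (Sections 8.1, 8.8 and 8.9).
- Hazard ratio 0.60, so |ln 0.60| = 0.5108 (Sections 8.1 and 8.9).
- D = 331 PFS events (Section 8.9, Table 13).
- Allocation 2:1, so the information factor is (2/3)(1/3) = 2/9 (Section 8.9).
- For methods that need event timing: exponential PFS with control median 2.5 months, 16 months of enrollment, about 6 months of minimum follow-up and about 10% dropout a year (Section 8.9). Uniform accrual is an assumption; the plan gives only the length of enrollment.

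**Step 1: Schoenfeld, which needs no accrual assumption**

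sqrt(331 × 2/9) = 8.576, and 0.5108 × 8.576 = 4.381.

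Power = Φ(4.381 − 2.878) = Φ(1.503) = 93.4%. This reproduces the 94% of Sections 8.1 and 8.9 to within a point.

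**Step 2: the boundary in the same row**

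exp(−2.878 / 8.576) = 0.715, consistent with the printed 0.71. The alpha, the event count and the boundary in that row therefore fit together; only the power does not.

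**Step 3: variance from expected events per arm**

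Monthly hazards are ln 2 / 2.5 = 0.2773 for control and 0.6 × 0.2773 = 0.1664 for pembrolizumab; dropout is −ln(0.9)/12 = 0.0088. At Month 22 this gives 126.7 control and 228.1 pembrolizumab events, 354.8 in total. Scaled by 331/354.8, they become 118.2 and 212.8.

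Power = Φ(0.5108 / sqrt(1/118.2 + 1/212.8) − 2.878) = Φ(4.453 − 2.878) = 94.2%. With a pooled variance under the null it is 93.7%.

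**Step 4: simulation**

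Two separate runs, each of 20,000 trials of 408 subjects, used an unstratified log-rank test at the 331st event. They gave 94.1% and 94.3% (Monte Carlo standard error about 0.16 points).

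**Step 5: can any variant reach 99% at alpha 0.20%?**

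| Variant | Power |
|---|---|
| Schoenfeld, 2:1, two-sided | 90.2% |
| Schoenfeld, 2:1, one-sided | 93.4% |
| Freedman, 1:1, one-sided | 95.3% |
| About 355 events at Month 22 instead of 331 | 95.4% to 95.9% |
| Schoenfeld, 1:1, one-sided | 96.2% |
| Freedman, 2:1, one-sided: Φ(sqrt(331 × 2) × 0.4/2.2 − 2.878) | 96.4% |

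None does. By Schoenfeld, 99% needs one of the following:

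- D = ((2.878 + 2.326)/0.5108)² × 9/2, about 467 events, more than the 408 subjects enrolled;
- a hazard ratio of about exp(−5.204/8.576) = 0.545;
- a one-sided alpha of about 2.0%, ten times the allocated level.

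Even if all 408 subjects had an event, power would be Φ(0.5108 × sqrt(408 × 2/9) − 2.878) = 97.6%.

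**Step 6: the other two rows**

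| Alpha | Schoenfeld | Events per arm | Simulation | Freedman 2:1 |
|---|---|---|---|---|
| 1.35% | 98.5% | 98.8% | 98.8% | 99.3% |
| 2.50% | 99.2% | 99.4% | 99.3% to 99.4% | 99.7% |

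The >99% at 2.50% is right. At 1.35% it depends on the formula, by at most half a point.

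**The case against.** The strongest objection is about weight. Nothing operational rests on this cell. The table's job is to set boundaries, and the boundary in the row is right. Section 8.9 sizes the trial on OS, not PFS. The correct 94% appears in the summary and in the power section, and footnote c sends the reader to the latter. On this view the slip is editorial. It is true that no analysis or decision changes. But the cell misstates an operating characteristic of a primary hypothesis and contradicts two other statements in the same plan, so it still has to be corrected.

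A second objection concerns the 1.35% row: three of the four methods fall just short of the printed >99%. That is fair, but the gap is half a point or less and one standard formula supports the entry, so it is not counted as an error here.

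Third, the simulations assume uniform accrual and omit the five analysis strata of Section 8.6.1.1, and uniform accrual would yield about 355 events by Month 22 rather than 331. These are real limits, but Schoenfeld's 93.4% does not use the accrual assumption, and 355 events still give no more than 95.9%.

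**Conclusion.** The concern holds. The 99.00% in Table 13 is wrong as written; the 94% in Sections 8.1 and 8.9 is right. With exactly 331 events, hazard ratio 0.60, 2:1 allocation and one-sided alpha 0.20%, the main methods give 93.4% to 94.3%. The type II error is thus 5.7% to 6.6%, against the 1.0% that the table implies. The conclusion does not depend on the choice of formula, since the most favourable one stops at 96.4%. The error is confined to the stated power; type I error control and the PFS decision rule are unaffected.

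**What to change.** In Table 13, change the power at alpha 0.20% from 99.00% to 94%. The alphas, the hazard ratio boundaries, the event count and the other two power cells need no change. The cost is one table cell; sample size and analyses stay as they are.

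Optionally, in the same edit, align the OS power at overall alpha 2.3%. Sections 8.1 and 8.9 say about 92%, while the 2.3% rows of Table 14 and the Section 8.8 text say 91% (Table 14 shows 92% at 2.5%). Writing about 91% in Sections 8.1 and 8.9 would remove the mismatch. One point is within the variation between methods, so this is labelling only.

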8.6.1.2 Overall Survival

The non-parametric Kaplan-Meier method will be used to estimate the survival curves. The hypotheses of treatment difference in survival will be tested by the stratified log -rank test. A stratified Cox proportional hazard model with Efron's method of tie handling will be used to estimate the magnitude of the treatment difference (i.e., the hazard ratio). The hazard ratio and its 95% confidence interval from the stratified Cox model with a single treatment covariate will be reported. The stratification factors used for randomization will be applied to both the stratified log-rank test and the stratified Cox model. The same 5 strata defined for the PFS analysis (see Section 8.6.1.1) will be used for the OS analysis.

Subjects in the control arm are expected to discontinue treatment earlier compared to subjects in the pembrolizumab arm, and may switch to another anti PD-1 treatment following the verification of progressive disease by blinded central imaging vendor review. Exploratory analyses to adjust for the effect of treatment switching to other PD-1 therapies on OS may be performed based on recognized methods, e.g. the Rank Preserving Structural Failure Time model proposed by Robins and Tsiatis [53], two-stage model, etc., based on an examination of the appropriateness of the data to the assumptions required by the methods.

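### Section 8.8 joins fixed effect sizes to the p-value bounds for PFS and ORR, and Table 15's ORR difference at alpha 1.15% should be about 6.1 points, not 5.8; the practical effect is small.

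*Combined protocol and SAP*

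**What the plan says.** Section 8.8 (Multiplicity) sets out how success is declared.

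- **PFS.** At alpha 0.2% the nominal p-value must be at most 0.002, "and the PFS hazard ratio should be" at most 0.71. Table 13 ties 0.71 to an expected 331 events.
- **ORR.** At alpha 0.2% the p-value must be at most 0.2%, "and the ORR percentage point difference (pembrolizumab-control) should be" at least 8.5 points. The plan says that "the ORR hypothesis can be tested at Type I error levels of" 0.2%, 1.15% or 2.5%, and Table 15 (titled as efficacy boundaries) gives 8.5, 5.8 and 5.0 points for them. Its footnote states: "The assumed expected ORR in pembrolizumab and control groups are 15% and 3%, respectively".
- **OS.** The hazard ratios are introduced as examples. The information fractions are to be adjusted to the events observed, and if the final count differs from 273, "a minor adjustment in the final bound may be required as well". No such wording accompanies the PFS or ORR figures.

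Sections 8.6.1.1 and 8.6.1.3 assign the tests: stratified log-rank for PFS, and stratified Miettinen-Nurminen for ORR.

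**The concern.** A fixed hazard ratio or a fixed difference in proportions is not equivalent to a p-value bound. The hazard ratio at the bound depends on the number of PFS events, and that number is only projected, because the analysis is triggered by OS events. The ORR difference at the bound depends on the observed control rate. If both conditions must hold, the stricter one decides, and a result significant at its alpha can be called a failure.

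This touches a primary endpoint and the alpha-controlled secondary endpoint. It also reaches OS, because rejecting both PFS and ORR at 0.2% raises the OS level from 2.3% to 2.5%.

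The 1.15% row of Table 15 is a separate matter. It is one of only three levels at which ORR may be tested, and its threshold does not match its alpha.

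**Working it through.** **Inputs.** 408 subjects (Section 8.9); "The study will randomize subjects in a 2:1 ratio into pembrolizumab arm and the control arm", hence 272 versus 136; control ORR 3% (Table 15 footnote); one-sided alphas as printed; 331 PFS events and a design hazard ratio of 0.60 (Section 8.9). The ORR calculations are unstratified.

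**1. Table 15.** The boundary is the difference d that solves

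d = z × sqrt[ p̄(1 − p̄)(1/272 + 1/136) ], with p̄ = 0.03 + 2d/3.

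| Alpha | z | Standard error at solution | d (points) | Printed |
|---|---|---|---|---|
| 0.20% | 2.878 | 0.02955 | 8.51 | 8.5 |
| 1.15% | 2.273 | 0.02694 | 6.13 | 5.8 |
| 2.50% | 1.960 | 0.02560 | 5.02 | 5.0 |

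The outer rows reproduce to the printed decimal and the middle row does not. The Miettinen-Nurminen factor N/(N − 1) gives 8.52, 6.14 and 5.03.

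Other methods do not recover the three printed values together. In row order, unpooled variance gives 6.66, 5.01, 4.20; continuity correction 9.28, 6.87, 5.74; arcsine 7.21, 5.37, 4.48; and 1:1 allocation 7.03, 5.17, 4.29. Using alpha 1.35% (a PFS level) in the middle row gives 5.9.

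In reverse, at d = 5.8 points p̄ = 0.0687, the standard error is 0.02656, z = 2.184 and p = 1.45%. Differences of 5.75 to 5.85 points correspond to 1.50% down to 1.40%, so rounding does not explain the cell. In whole responders, 24/272 versus 4/136 is 5.9 points with p = 1.35%.

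**2. ORR joint condition at alpha 0.2%.** With z = d / sqrt[ p̄(1 − p̄)(1/272 + 1/136)(408/407) ], the smallest significant results are:

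| Control responders of 136 | Pembrolizumab responders of 272 | Difference (points) | p |
|---|---|---|---|
| 0 | 16 | 5.9 | 0.198% |
| 1 | 21 | 7.0 | 0.16% |
| 2 | 25 | 7.7 | 0.16% |
| 3 | 28 | 8.1 | 0.18% |
| 4 | 32 | 8.8 | 0.15% |

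For 28 versus 3: p̄ = 31/408 = 0.0760, the standard error is 0.02786, d = 0.0809, z = 2.90 and p = 0.18%. The first four rows meet the p-value bound and fail 8.5 points. With four control responders the smallest significant difference already exceeds 8.5, and with five to eight it is 9.2 to 10.3. The extra condition therefore binds only with three or fewer control responders.

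Exact binomial enumeration, p alone versus both conditions:

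- 15% versus 3% (plan): 86.2% versus 85.8%.
- 12% versus 3% (assumed): 57.0% versus 52.7%.
- 12% versus 2% (assumed): 78.0% versus 71.1%.
- 10% versus 1% (assumed): about 80% versus 57%.

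**3. PFS joint condition at alpha 0.2%.** The standard error of the log hazard ratio is 1/sqrt(331 × 2/9) = 0.1166.

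- Hazard ratio at the bound: exp(−2.878 × 0.1166) = 0.715, against the printed 0.71.
- p at hazard ratio 0.71: −ln(0.71)/0.1166 = 2.94, so p = 0.17%.
- Power at hazard ratio 0.60 on p alone: Φ[(ln 0.7149 − ln 0.60)/0.1166] = 93.4%, close to the 94% of Section 8.9.
- Power with the hazard ratio condition added: Φ[(ln 0.71 − ln 0.60)/0.1166] = 92.6%.

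The 0.71 condition binds from about 318 events upward. At an assumed 355 events the bound is 0.723, and power is 95.1% versus 93.3%.

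**The case against.** The best defence is that the effect sizes are only the p-value bounds translated to the effect scale. Section 8.8 says its tables show thresholds corresponding to each alpha. Testing is assigned to the log-rank and Miettinen-Nurminen statistics, and the Cox hazard ratio is for estimation. That is probably what was meant. It makes this a matter of wording, but it does not remove the problem: both sentences say what is needed to declare success, join the two conditions, and lack the example wording used for OS.

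Much of the rest of the defence stands. The PFS gap at 331 events is two-decimal rounding of 0.7149. The ORR condition excludes nothing significant once controls have four responders, and 3% of 136 is 4.1. The larger ORR losses rest on response rates that the plan does not give.

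A reader might infer more than the documents support:

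- **That Type I error is inflated.** An added condition can only make a test stricter.
- **That the 5.8 cell causes wrong decisions.** At a 3% control rate it is looser than the p-value bound, so it blocks no significant result there. It creates no false success either: 24/272 versus 4/136 still fails on p. The joint sentence is also written only for alpha 0.2%.
- **That the OS hazard ratios share the defect.** They are correct to two decimals, labelled as examples, and subject to stated adjustment.

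**Conclusion.** The text is wrong as written, with a small practical effect.

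The 1.15% cell of Table 15 should be about 6.1 points. That figure assumes an observed control rate of 3% and no stratification, whereas the planned test is stratified. The boundary moves with the control rate, to about 5.5 points at 2% and 6.6 at 4%. The case for correcting the cell is that the same assumptions reproduce the other two rows. The error misstates a boundary and does not change a decision at the planned control rate.

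The joint conditions, taken literally, cost about 0.8 percentage points of PFS power at 331 events (93.4 − 92.6) and about 0.4 points of ORR success at the planned rates (86.2 − 85.8). The PFS gap widens if more than 331 events accrue. The ORR loss grows if response rates are lower than planned.

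**What to change.** In Section 8.8:

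1. State that the p-value bound from the planned stratified test, computed on the data at the analysis, is the sole success criterion for PFS and for ORR.
2. Replace the joined effect-size conditions by a statement that the hazard ratios in Table 13 and the differences in Table 15 are approximate values at 331 events and at a 3% control rate.
3. Change the 1.15% row of Table 15 from 5.8% to about 6.1%, or to the value from the sponsor's own program with its assumptions stated.

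Make the third change together with the first two. If 6.1 were read as a further condition, it would fail results such as 22/272 versus 3/136 (8.09 − 2.21 = 5.88 points, p = 0.98%), which are significant at 1.15%.

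The cost is a sentence or two and one table cell. Design, sample size, alpha allocation and analysis methods do not change, and the OS text and Table 14 need no edit on this point.
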